The primary hypothesis is that there is a better anesthetic stability in the deep NMB group (Group 2) and that this is translated as a reduction of the BIS signal variability and a reduction in the required effect-site concentrations of propofol and remifentanyl (representative of the total drug consumption).

b) Secondary objectives

As a secondary objective, we will study the quality of recovery using the PQRS scale to see if maintaining a deep NMB level during surgery has an impact on the patients' quality of recovery.

The secondary hypothesis is that the quality of recovery (PQRS test) is better in the patients of Group 2.

Can adequacy of anesthesia depth and quality of recovery be influenced by the level of neuromuscular blockade?

6. Study design

Patients subjected to anterior cervical spine surgery under general intravenous anesthesia will be randomized to receive one of two protocols regarding the neuromuscular blockade:

- Group 1 – Standard Clinical Practice Group - standard NMB, with a standard rocuronium dose for intubation (0.6 mg/kg). If required, the reversal of neuromuscular block is performed with neostigmine.
- Group 2 – Deep NMB group - with a standard rocuronium dose for intubation (0.6 mg/kg), followed by a constant infusion of rocuronium (10-15 µg/kg/min) to guarantee a PTC less or equal to 2 on the TOF monitor (PTC is evaluated every 5 minutes). The reversal of neuromuscular block is performed with Sugammadex (4 mg/kg).

a) Primary Endpoints

- BIS signal variability using the measured standard deviation during the maintenance phase of anesthesia
- Required effect-site concentrations of remifentanyl and propofol

b) Secondary Endpoints

- PQRS results at 15 and 40 minutes after surgery (taking into account the patient baseline values of the PQRS test done on the pre-anesthetic visit)
- PQRS results at day 3 after surgery

c) Study type

This is an interventional, phase 4, double-arm, parallel, randomized, open-label, single-center study aiming to compare two anesthesia protocols.

Can adequacy of anesthesia depth and quality of recovery be influenced by the level of neuromuscular blockade?

d) Study Timeline

- Study Start Date: April 2016
- Study End Date: April 2017
- First Patient In: April 2016
- Last Patient In: April 2017
- Last Patient Out: April 2017
- Study Analysis: May 2017
- Publication: November 2017

Can adequacy of anesthesia depth and quality of recovery be influenced by the level of neuromuscular blockade?

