- If no EMG activity is present, the propofol effect-site target concentration is increased by steps of 0,5 µg/ml until the concentration required for loss of consciousness is achieved.

Response Protocol to Mean Arterial Pressure (MAP) values outside the target interval:

- If MAP is more than 30% below the baseline value, an ephedrine bolus of 5 mg is given every 3 minutes until the desired effect;
- If MAP is more than 30% above the baseline value, the remifentanil effect-site target concentration is increased by steps of 1,5 ng/ml until a maximum of 15 ng/ml is achieved. If the MAP value does not decrease to the desired range, then the propofol effect-site target concentration is increased by steps of 0,5 µg/ml until the value required for loss of consciousness is achieved;
- If the MAP still is outside the desired interval, then a 10 mg dose of Labetalol should be administer every 10 minutes until the desired effect.

If the MAP does not respond to the previous protocol steps, then the study should be stopped.

Additional rocuronium (muscle relaxant) bolus of 0.2 mg/kg are allowed in the following situations:

Can adequacy of anesthesia depth and quality of recovery be influenced by the level of neuromuscular blockade?

- If during surgery, the surgeon mentions difficulties due to muscle contraction
- If the patient is showing spontaneous ventilation that prevents adaptation to mechanical ventilation

i. Assessment 3

Assessment name: 15 minutes PQRS Test

Timing: Day 1, time 2: 15 minutes after surgery

PQRS test
(Serious) Adverse Events

After the patient is moved from the surgery room to the recovery room, the PQRS test is performed in both groups at 15 minutes post-surgery. The PQRS tests are recorded in the patient's individual CRF forms.

ii. Assessment 4

Assessment name: 40 minutes PQRS test

Timing: Day 1, time 3: 40 minutes after surgery

PQRS test
(Serious) Adverse Events

The PQRS test is performed in both groups of patients at 40 minutes post-surgery.

Can adequacy of anesthesia depth and quality of recovery be influenced by the level of neuromuscular blockade?

The main study finishes after the 40 minutes PQRS test is performed.

iii. Assessment 5

Assessment name: Follow-up

Timing: 3 days after surgery

(Serious) Adverse Events
Patient Satisfaction evaluation

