At the 3rd day after surgery a telephone contact is made to identify the occurrence of any Adverse Event (AE) (according to Good Clinical Practice (GCP) guidelines and pharmacovigilance directives), as well as to evaluate patient satisfaction using only the PQRS questions that address this issue. If at the 3rd day after surgery the patient is still in the hospital, than the contact is performed face to face by the investigator or designated researcher. The overall data acquisition for each patient ends at this point.

The occurrence of SAE and AE is noted on the specific forms on the patient individual CRF and acted accordingly to the GPC guidelines.

The individual patient data will be anonymized after the 3rd day contact.

iv. Discontinuation Visit

(Serious) Adverse Events
Patient Satisfaction evaluation

Can adequacy of anesthesia depth and quality of recovery be influenced by the level of neuromuscular blockade?

c) Compliance with study treatment

Protocol compliance will be monitored, including accurate prescription and administration of study treatment according to protocol.

Study treatment (IMP and NIMP) will be supplied and administered by medical personnel, so no compliance issues are expected to occur.

d) Concomitant and prohibited medication

Allowed concomitant medication and prohibited medication are those described by the SoPC of the IMP and NIMPs.

e) Expenses and benefits

Participants in the study are not expected to have additional expenses due to their study participation, since treatment and follow-up are similar to standard practice. Participants may benefit from the close monitoring due to study design.

Unscheduled visits travel expenses (until 3 days after discharge) will be reimbursed by the Sponsor (up to € 30) against expenditure presentation document).

Can adequacy of anesthesia depth and quality of recovery be influenced by the level of neuromuscular blockade?

9. Efficacy evaluation

a) Efficacy measure

A 25% reduction on the BIS variability (standard deviation) is considered clinically relevant.

b) Methods

All hemodynamic and brain monitoring, TOF monitoring, and infusion pumps data will be recorded online during surgery with a sample time of 5 seconds, using data collection software on a laptop connected to all monitors and infusion pumps.

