Data collection software (Rugloop® Software and TOF Link) are installed on a Laptop computer connected to the Base Primea infusion pumps, the BIS monitor, GE monitor and TOF Watch monitor, allowing for all data to be recorded online. The patient data files generated by the Rugloop® software will be accessed using the Labgrab® software and exported to excel files. TOF watch data will also be exported to excel files. All online data is posteriorly recorded in a patient individual CD. All non-electronic data will be noted on the patients' paper CRF and on the RugLoop® software notes toolbar.

The total doses of ephedrine and labetalol are used as a surrogate variable, since they are the drugs used in the response protocol to hemodynamic instability (MAP being outside the desired target range).

The following recorded data will be analyzed per patient and compared between the two study groups:

- BIS signal variability using the measured Standard deviation during the maintenance phase of anesthesia
- BIS average value during the maintenance phase of anesthesia
- Duration of periods of BIS values above 60 and below 40
- Average effect-site concentrations of propofol and remifentanil required during the maintenance of anesthesia
- Total doses of remifentanil, propofol, ephedrine and labetalol

Can adequacy of anesthesia depth and quality of recovery be influenced by the level of neuromuscular blockade?

- PQRS results at 15 and 40 minutes after surgery (taking into account the patient baseline values of the PQRS test done on the pre-anesthetic visit)
- Patient satisfaction evaluated using the specific PQRS questions

Can adequacy of anesthesia depth and quality of recovery be influenced by the level of neuromuscular blockade?

10. Safety evaluation

Each patient is considered to have ended participation in the study when he/she has completed the last telephone contact at 3 days post-surgery to verify the occurrence of any adverse events (AE) according to the pharmacovigilance guidelines, or prematurely discontinues from the trial.

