Where the determination of AE severity rests on medical judgment, the determination of severity must be made with the appropriate involvement of a medically-qualified investigator.

Can adequacy of anesthesia depth and quality of recovery be influenced by the level of neuromuscular blockade?

The severity of AEs will be graded according to the following definitions:

Mild: awareness of sign, symptom, or event, but easily tolerated;

Moderate: discomfort enough to cause interference with usual activity and may warrant intervention;

Severe: incapacitating with inability to do normal daily living activities or significantly affects clinical status, and warrants intervention;

Assessment of Causality

A medically qualified investigator must assess the relationship of any AE (including SAEs) to the use of the investigational product, as unlikely related, possibly related, or probably related, based on available information, using the guidelines listed below:

Unlikely related: no temporal association, or the cause of the event has been identified and attributed to other disease or drug; or the drug, biologic, or device cannot be implicated based on available information;

Possibly related: temporal association, but other etiologies are likely to be the cause; however, involvement of the drug, biologic, or device cannot be excluded based on available information;

Probably related: temporal association, other etiologies are possible, but unlikely based on available information.

Can adequacy of anesthesia depth and quality of recovery be influenced by the level of neuromuscular blockade?

11. Statistics

a) Methods

Differences in age, weight, and height between the groups will be analyzed with t-test.

Continuous data will be analyzed using independent samples t test, or RM ANOVA for repeated measurements.

Univariate analyses will be conducted using chi-square analysis or Fisher exact test where appropriate, to analysis de PQRS recovery result at discrete time points, and repeated measures ANCOVA for continuous data.

Statistical analysis of the subcategories of the PQRS test will be performed using the Cochran Mantel – Haenszel test on the proportions of recovery for each group with continuity correction over two measurement periods.

b) Number of participants

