Sample size calculation with a power of 0.80 and an α of 0.05, considering the primary hypothesis of a reduction in the BIS variability (measured as the standard deviation) and a reduction in the propofol and remifentanil drug consumption (measured as the average effect-site concentration required) during maintenance of anesthesia.

To estimate the standard deviation of our population, we searched our database for standard clinical practice cases with: online data recording; cervical spine surgery; BIS average values within the recommended target values [40-60]; TCI anesthesia with propofol and remifentanil.

A total of 12 patients data were analyzed (mainly due to the lack of online recording during the procedures), the average BIS standard deviation was 8.7 ± 3.14 , and the average propofol and remifentanil effect-site concentrations were 2.68 ± 0.9 $\mu\text{g/ml}$ and 2.83 ± 0.8 ng/ml , respectively.

Can adequacy of anesthesia depth and quality of recovery be influenced by the level of neuromuscular blockade?

A 25% reduction on the BIS variability (standard deviation) was considered clinically relevant, and gave a minimum sample size of 26 per group.

A reduction on propofol average effect-site concentration of 20% was considered clinically relevant, and gave a minimum sample size of 34 per group.

A reduction on remifentanil average effect-site concentration of 20% was considered clinically relevant, and gave a minimum sample size of 24 per group.

Considering the above results and the possibility of patient exclusion due to external complications during surgery, a total of 35 patients per group will be included in the study.

The secondary variable, result of the PQRS test was not used in the sample size calculation, since there are no studies on the comparison of recovery after two different interventions and the data regarding sample calculation that the authors of PQRS showed us are for the recovery at 3 days post-surgery, which is not comparable to our study. Therefore we did not consider adequate to estimate a percentage difference for which we do not know the clinical reality.

The surrogate variables, consumption of ephedrine and labetalol will be analyzed since these drugs are used in the response protocol to target deviations, but they are not considered for the sample size calculation.

c) Level of statistical significance

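### Stratified by time point, the Cochran-Mantel-Haenszel test for the PQRS subcategories ignores that the same patients are in both strata, so its type I error can exceed 5%

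*Combined protocol and SAP*

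**What the plan says.** Section 11 a) gives one sentence on the PQRS subcategories. It plans a Cochran-Mantel-Haenszel (CMH) analysis, described as the "Haenszel test on the proportions of recovery for each group with continuity correction over two measurement periods". The strata are not named and neither are the two periods. Section 11 a) also plans chi-square or Fisher tests at single time points. It names repeated-measures methods (RM ANOVA, ANCOVA) only for continuous data.

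Section 6 b) lists as secondary endpoints "PQRS results at 15 and 40 minutes after surgery", taking baseline into account, and "PQRS results at day 3 after surgery". Under Assessment 4 in section 8 b), "The PQRS test is performed in both groups of patients at 40 minutes post-surgery", so the patients tested at 15 minutes are tested again. The day-3 contact (Assessment 5) is to "evaluate patient satisfaction using only the PQRS questions that address this issue". The list in section 9 b) opens with "The following recorded data will be analyzed per patient and compared between the two study groups". For PQRS it contains only the 15- and 40-minute results and "Patient satisfaction evaluated using the specific PQRS questions".

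For PQRS, section 11 b) gives no expected difference: "Therefore we did not consider adequate to estimate a percentage difference for which we do not know the clinical reality".

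**The concern.** The secondary hypothesis in section 5 b) is that recovery is better in Group 2, so the test has to compare the groups. A CMH test that does this over two measurement periods takes the periods as strata. CMH assumes that different strata hold independent subjects. Here each patient appears in both strata, and a patient who has recovered in a domain at 15 minutes is likely to be recovered at 40 minutes too. With positive correlation the summed variance is too small, and a group difference in a subcategory can be declared too readily.

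The two periods are probably 15 and 40 minutes, because section 8 b) limits day 3 to satisfaction questions. Section 6 b) and the flow-chart in section 6 e) nevertheless place a PQRS assessment at day 3. The dependence exists whichever two are meant. PQRS is the trial's only named secondary endpoint, and section 17 plans a separate paper on the secondary objective.

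**Working it through.** The protocol states no error rate, power or sample size for this test, so there is no figure to reproduce.

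**Inputs**
- From the protocol: 35 patients per group (n = 35, N = 70; section 11 b); significance at p below 0.05 (section 11 c); continuity correction and two periods (section 11 a).
- Assumed, because the protocol gives neither: the recovery rates p1 and p2 at the two times, equal in both groups under the null, and phi, the correlation between a patient's two yes/no results.

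**Step 1: the missing term.** Let V1 = p1(1−p1) and V2 = p2(1−p2). The ratio of the true variance of the CMH numerator to the variance the test uses is

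1 + 2·phi·√(V1·V2)/(V1+V2).

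This is about 1 + phi when V1 and V2 are similar. For 30% then 50%, V1 = 0.21 and V2 = 0.25, so the ratio is 1 + 2·phi·0.2291/0.46 = 1 + 0.996·phi. For 5% then 50% it is 1 + 0.73·phi.

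**Step 2: normal approximation for 30% then 50%.** The test's variance is about (n²/N)(V1+V2) = 17.5 × 0.46 = 8.05, an SD of 2.837. With the 0.5 correction it rejects when the numerator exceeds 1.96 × 2.837 + 0.5 = 6.061 in absolute value.
- phi 0: true SD 2.837, z = 6.061/2.837 = 2.136, error about 3.3%.
- phi 0.3: true variance 8.05 × 1.299 = 10.456, SD 3.234, z = 1.874, error about 6.1%.
- phi 0.5: true variance 8.05 × 1.498 = 12.060, SD 3.473, z = 1.745, error about 8.1%.

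The continuity correction makes the test conservative at phi 0. The missing covariance uses up that margin and then exceeds it.

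**Step 3: exact enumeration** of the two-sided null rejection probability, with correction, 35 per group:

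| Rates | phi 0 | phi 0.2 | phi 0.3 | phi 0.5 | phi at which 5% is passed |
|---|---|---|---|---|---|
| 50% / 50% | 3.4% | 5.3% | 6.4% | 8.4% | 0.17 |
| 50% → 60% | 3.3% | 5.1% | 6.1% | 8.2% | 0.19 |
| 30% → 50% | 3.1% | 4.9% | 5.9% | 7.8% | 0.21 |
| 20% → 30% | 3.0% | 4.8% | 5.7% | 7.7% | 0.23 |
| 10% → 20% or 80% → 90% | 2.8% | 4.4% | 5.2% | 7.1% | 0.28 |
| 10% / 10% or 90% / 90% | 2.4% | 4.0% | 4.8% | 6.6% | 0.33 |
| 5% → 10% | 2.0% | 3.2% | 4.0% | 5.6% | 0.44 |
| 5% / 5% or 95% / 95% | 1.4% | 2.4% | 2.9% | 4.3% | 0.60 |
| 2% / 2% or 98% / 98% | 0.1% | 0.4% | 0.6% | 1.0% | never (at most 3.3%) |

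**Step 4: steep rises.** The two rates cap phi at √[p1(1−p2)/((1−p1)p2)] for p1 < p2. For 10% → 70% this is √(0.03/0.63) = 0.22. Error at the largest attainable phi:
- Below 5%: 10% → 90% (phi 0.11) 3.3%; 5% → 50% (0.23) 4.2%; 10% → 70% (0.22) 4.6%.
- Just above 5%: 20% → 80% (0.25) 5.1%.
- Clearly above 5%: 10% → 50% (0.33) 5.6%; 30% → 70% (0.43) 7.4%.

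**Step 5: adding the covariance.** With t1 and t2 the total numbers recovered at each time and t12 the number recovered at both, add 2f(t12 − t1·t2/N) to the CMH variance, where f = n²/(N(N−1)). With complete data this equals the permutation variance of the number of time points recovered per patient (0, 1 or 2), and the numerator is unchanged. In nine simulated scenarios (400,000 trials each, rates of 10% to 90%, phi 0.2 to 0.7), error was 4.7% to 5.0% without continuity correction and 2.3% to 3.5% with it. For 50% → 60% at phi 0.5, the planned test gave 8.1% and the adjusted test 5.0% or 3.5%.

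**The case against.** The strongest objection is that the premise is inferred. The sentence in section 11 a) speaks of proportions for each group, which could mean comparing the two periods within each group with patients as strata. That is a valid paired use of CMH, and the inflation then disappears. The list in section 9 b) does not say which test makes which comparison. This stands as a reason to call the reading natural rather than certain. But the within-group reading would not test whether recovery is better in Group 2, so the plan would then have no between-group subcategory test across the two periods.

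Second, no harm is shown for this trial. Rates and phi are unknown, and the planned test is conservative at low phi. That is correct, and it makes the point conditional.

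Third, dropping the continuity correction is a separate choice from adding the covariance, and it makes the new test less conservative at low phi (for 30% → 50% at phi 0, about 5.0% against 3.1%). That also stands, so the fix treats the two separately. The choice among a permutation test, GEE and a covariance-adjusted CMH is partly preference.

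**Conclusion.** The concern holds, as a minor and conditional point. If the periods are the strata, the planned test omits the within-patient covariance and nothing else in the protocol supplies it for binary PQRS data. With 35 per group, error passes 5% at phi of 0.17 to 0.33 for rates of 10% to 90% with modest change, and reaches 6.6% to 8.4% at phi 0.5. It may not pass 5% if recovery is rare, nearly universal or rises steeply.

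These figures rest on assumed rates and correlations, so the inflation in this trial is unknown and could be nil. Only the PQRS subcategory analysis is affected. The primary endpoints, the sample size and the chi-square or Fisher tests at single time points are not.

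**What to change.** In section 11 a):
- Name the stratifying variable and the two measurement periods, consistently with sections 6 b), 6 e), 8 b) and 9 b).
- Replace the time-stratified CMH test with one whose variance allows for repeated measures on a patient. One option is to compare the number of time points recovered per patient (0, 1 or 2) between groups with a permutation variance.
- State whether a continuity correction is used. Without it, simulated error was 4.5% to 5.2% where at least one rate was 10% or more, apart from small departures at extreme phi (4.4% for 5% → 10% at its maximum phi, 5.7% for 10%/10% at phi 1). With it, error is 2.2% to 3.6% at rates of 10% or more.
- Specify the exact version for very rare outcomes. At 5%/5% the large-sample version ran from 5.5% (phi 0) to 3.2% (phi 0.6). The exact version gave 0.8% to 1.4%, which is valid but conservative.
- State how a patient with one missing time point is handled.
- Keep the tests at single time points.

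The cost is a few sentences, standard software and no new data, plus the submission to the competent authorities that section 11 f) requires for any change to the statistical plan. P-values may move either way. For 30% → 50% with no group difference, the uncorrected new test alone rejects in 1.9%, 0.1% and 0.0% of trials at phi 0, 0.3 and 0.5. The planned test alone rejects in 0.0%, 1.0% and 2.9%.

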The sample was calculated at a significance level of 95%. A p-value below 0.05 is considered statistically significant.

d) Study termination

Data analysis is planned for the end of the trial. No early study termination is planned.

Can adequacy of anesthesia depth and quality of recovery be influenced by the level of neuromuscular blockade?

e) Missing data

Participants with missing primary endpoint data will not be included in the analysis.

f) Deviations

Any change to the statistical plan will be submitted to the competent authorities prior to its implementation.

g) Inclusion in analysis

All data will be included for the analysis (Intention to treat).

Can adequacy of anesthesia depth and quality of recovery be influenced by the level of neuromuscular blockade?

12. Direct access to source documents

The investigator will grant direct access to paper and/or electronic documentation pertaining to the clinical study (e.g. CRFs, source documents such as hospital patient charts and investigator study files) to authorized individuals, as the clinical trial monitors, auditors or health authority inspections. The objective of these accesses is to ensure the trial is being conducted according to local laws and regulations and ICH-GCP.

All site facilities related to the study conduct can be visited during an audit (e.g. pharmacy, laboratory, archives).

The investigator agrees to co-operate and provide assistance at reasonable times and places with respect to any monitoring or auditing activity.

Can adequacy of anesthesia depth and quality of recovery be influenced by the level of neuromuscular blockade?

13. Quality control and quality assurance

The study will be conducted in accordance with the current approved protocol, ICH GCP, relevant regulations and standard operating procedures.

Regular monitoring will be performed according to ICH GCP. Data will be evaluated for compliance with the protocol and accuracy in relation to source documents. Following written standard operating procedures, the monitors will verify that the clinical trial is conducted and data are generated, documented and reported in compliance with the protocol, GCP and the applicable regulatory requirements.

Inspections and Audits

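### Sidedness is not declared: the stated sample sizes fit a one-sided 5% test, and under a two-sided 0.05 t-test 35 per group gives about 69% power for propofol, not 80%

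*Combined protocol and SAP*

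**What the plan says.** Section 11 b) opens with "Sample size calculation with a power of 0.80 and an α of 0.05". The variability estimates come from the site's own records: "A total of 12 patients data were analyzed". They gave a BIS standard deviation of 8.7 ± 3.14, and "the average propofol and remifentanil effect-site concentrations were 2.68 ± 0.9" µg/ml for propofol, with 2.83 ± 0.8 ng/ml for remifentanil.

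Three minimum sizes follow:

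- BIS variability, 25% reduction: "gave a minimum sample size of 26 per group".
- Propofol, 20% reduction: "A reduction on propofol average effect-site concentration of 20% was considered clinically relevant, and gave a minimum sample size of 34 per group".
- Remifentanil, 20% reduction: "gave a minimum sample size of 24 per group".

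The planned 35 per group is meant to cover these minimums and some exclusions.

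On the analysis, section 11 a) says "Continuous data will be analyzed using independent samples t test", with no mention of a transformation. Section 11 c) says "The sample was calculated at a significance level of 95" per cent and sets the threshold at p below 0.05. No section declares a one- or two-sided test.

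Sections 5 a), 6 a) and 11 b) treat the propofol concentration as part of the primary hypothesis or as a primary endpoint. The synopsis names only BIS variability as the primary endpoint.

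**The concern.** A threshold of p below 0.05 with an independent-samples t-test is normally read as two-sided. On that reading all three stated minimums are too small for the plan's own inputs. Propofol matters most, because its 34 is the largest of the three and so drives the choice of 35.

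Two things are at stake. First, the stated 80% power would not hold for propofol. Second, the decision rule for the primary endpoints is left open in an open-label trial: the same data could be called significant or not, depending on a choice that the plan does not record.

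**Working it through.** **Inputs (section 11 b).** Alpha 0.05, power 0.80, equal groups. Standardised effects d = (relative reduction × mean) / SD:

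- BIS variability: 0.25 × 8.7 / 3.14 = 2.175 / 3.14 = 0.693
- Propofol: 0.20 × 2.68 / 0.9 = 0.536 / 0.9 = 0.596
- Remifentanil: 0.20 × 2.83 / 0.8 = 0.566 / 0.8 = 0.708

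**Reproducing the stated sizes.** The normal formula is n per group = 2 (z_alpha + z_power)² / d². The t-test figures use the noncentral t distribution and are the smallest whole n that reaches 80%.

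| | BIS SD | Propofol | Remifentanil |
|---|---|---|---|
| Stated in the plan | 26 | 34 | 24 |
| One-sided 5%, normal (z sum 1.645 + 0.842) | 25.8 | 34.9 | 24.7 |
| One-sided 5%, t-test | 27 | 36 | 26 |
| Two-sided 5%, normal (z sum 1.960 + 0.842) | 32.7 | 44.3 | 31.4 |
| Two-sided 5%, t-test | 34 | 46 | 33 |

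The one-sided normal formula rounds up to exactly 26 for BIS variability, whose SD is printed to two decimals. It is within one patient of the stated figures for the two drugs, whose SDs are printed to one decimal. An unrounded propofol SD of 0.888 gives 33.9, and a remifentanil SD of 0.788 gives 24.0. The two-sided t-test figures exceed the stated ones by 8, 12 and 9 patients per group.

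**Power at 35 per group (t-test, printed SDs).**

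| | BIS SD | Propofol | Remifentanil |
|---|---|---|---|
| One-sided 5% | 89.0% | 79.4% | 90.1% |
| Two-sided 5% | 81.5% | 69.0% | 83.1% |

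**Does rounding of the SDs explain the gap?** A printed 0.9 stands for 0.85 to 0.95. Two-sided propofol power is 73.9% at 0.85 and 64.3% at 0.95, and even at 0.85 the two-sided t-test needs 41 per group. Reaching 80% at 35 per group requires an SD of 0.79 or less, which is outside the range. For remifentanil, an SD of 0.75 to 0.85 gives 87.5% to 78.4%.

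**Detectable effect.** At 35 per group, 80% two-sided power needs d = 0.679. For propofol this is 0.679 × 0.9 / 2.68 = 22.8% (21.5% to 24.1% over the rounding range), against the planned 20%.

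**Where sidedness decides the result.** The standard error for propofol is 0.9 × √(2/35) = 0.215. Critical t values on 68 df are 1.668 (one-sided) and 1.995 (two-sided). The smallest significant reductions are therefore 0.359 / 2.68 = 13.4% and 0.429 / 2.68 = 16.0%. If the true effects are those planned, the chance of landing between the two thresholds is the difference between the two powers: 10.4% for propofol, 7.4% for BIS variability and 7.0% for remifentanil.

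**Precision of the pilot SD.** Assuming normality, 12 patients (chi-square, 11 df) give a 95% interval for the propofol SD of about 0.64 to 1.53. Two-sided power at 35 per group then runs from about 93% down to 30%.

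**The case against.** The strongest reply is that no arithmetic error has been shown. All the hypotheses are worded as reductions, nothing declares a two-sided test, and a one-sided 5% formula reproduces the stated sizes with propofol power close to 80%. That is a plausible account of how the sizes arose. It does not remove the gap, because a one-sided test is declared nowhere.

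A second reply is that a two-sided calculation on the log scale also comes close. With SD = √ln(1 + CV²) and effects ln 0.75 and ln 0.80, the normal formula gives 23.2, 33.7 and 24.2, that is 24, 34 and 25 per group, and propofol power at 35 is 80.4%. One-sided intent is therefore inferred, not proven. The log version fits BIS variability less well (24 against 26), and section 11 a) describes no transformation. If it was intended, it too has to be written down.

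It is also fair that the shortfall at the printed SDs is confined to propofol, and that BIS variability, the only primary endpoint in the synopsis, keeps more than 80%. That margin is thin. Section 11 e) leaves out participants with missing primary data, and with 33 evaluable per group two-sided power is 79.1% for BIS variability, 66.4% for propofol and 80.8% for remifentanil.

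**Conclusion.** The concern holds. Sidedness is undeclared, and the stated 26, 34 and 24 per group fit a one-sided 5% raw-scale calculation and not a two-sided one. Read two-sided at 0.05, the design has about 69% power for a 20% propofol reduction (64% to 74% for SD rounding), so the chance of missing that effect is about 31% instead of 20%.

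This rests on the untransformed t-test that the plan describes, equal SDs in both groups, the printed pilot values and all 35 per group being evaluable. The rounding range does not include the sampling uncertainty of an SD taken from 12 patients, which is much wider. The powers are for each endpoint separately. The point must be settled before analysis, because the choice can reverse the result for a primary endpoint.

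**What to change.** Keep 35 per group and amend section 11 before any analysis:

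1. In 11 b) and 11 c), declare the tests two-sided at 0.05.
2. In 11 b), restate the required sizes as 34 (BIS variability), 46 (propofol) and 33 (remifentanil) per group, and the power at 35 per group as about 81.5%, 69% and 83%. Compute the final figures from the unrounded pilot SDs, and give the power at the expected evaluable number as well.
3. Add that propofol has 80% power for a reduction of about 23%, and that the SDs come from 12 patients.
4. If a one-sided 5% test is truly intended, declare it in both places and recompute the t-test minimums from the unrounded SDs: about 27, 36 and 26 at the printed values, with 32 to 40 for propofol over the rounding range.
5. If a log-scale analysis was intended, declare it in 11 a) and show the calculation.

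The cost is wording only, with no extra patients. Section 11 f) already requires changes to the statistical plan to go to the competent authorities before they are implemented. The drawback is that the stated propofol power becomes less favourable under the two-sided option.
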